19-005486

Pilot Study for the Treatment of Papillary Thyroid Carcinoma with
Radiofrequency Ablation

NCT04129411

Document Date: 10/02/2019

IRB Greater Than Minimal Risk Protocol

Principal Investigator: [name]

Co-Investigators: [name]., PhD. [name] and [name]., MBA

Study Title: Pilot study for the Treatment of Papillary Thyroid Carcinoma with Radiofrequency Ablation

Protocol version number and date: 1; 10/2/2019

Research Question and Aims

Hypothesis:

RFA can control or eliminate small papillary thyroid carcinoma.

Aims, purpose, or objectives:

We aim to study the changes in primary tumor volume, development of lymph node involvement, development of distant metastasis and changes in serum thyroid hormone levels in patients with papillary thyroid carcinoma following RFA therapy. We will also assess the stability of these changes (need for repeat therapy) and the safety of the RFA procedure.

General Background:

US population has a high prevalence of thyroid nodules, with 50% of individuals after the age of 50% having at least one such lesion if ultrasound studies are performed. About 5-8% of these lesions harbor a thyroid cancer of which 80% are differentiated papillary thyroid carcinoma.

The incidence of diagnosed papillary thyroid carcinoma (PTC) has increased over the recent decades and this diagnosis is typically followed by partial or total thyroidectomy. In a minority of these patients when the tumor size is < 10-15 mm the necessity of intervention is less clear. The majority of these cases are treated surgically, with a minority observed and few treated with intra-lesional ethanol injection.

Surgery implies removal of (at least) half of the thyroid with risk of surgical complications, a neck scar and a high likelihood of developing hypothyroidism (50-80%) with subsequent lifelong thyroid hormone therapy. However for these patients RFA opens new horizons. It has the ability to destroy the cancerous lesion (ref review (1) and avoids the development of hypothyroidism (none noted in our series of RFA therapy for much larger benign thyroid nodule (2). Adding to that the benefit of avoiding surgical complications and a scar on the neck is a powerful motivator for patients to seek this therapy.

Background on Radiofrequency Ablation (RFA)

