During the past ten years, radiofrequency ablation (RFA) has been shown to be a promising and well-tolerated new approach to benign TNs by inducing tissue necrosis and fibrosis through heat (3). Randomized trials in Italy and South Korea reported a 50% to 80% volume reduction in treated TNs, with sustained results 3 years after the intervention (3-6). In the United States, RFA is commonly used for percutaneous treatment of tumors in the lung, liver, kidney and bone (7). Yet until recently this intervention has not been validated for treating

benign or malignant TNs in North American Population. A year ago we have reported on our significant positive results with RFA on benign and toxic thyroid nodules in the past. Our results indicate substantial volume reduction of TNs by approximately 45% at 3 to 6 months, alleviation of compressive symptoms, and improvement in aesthetic appearance while preserving normal thyroid function.

Owing to advantages such as less invasiveness, reduced morbidity, lower complication rates, suitability for real-time imaging guidance and the ability to be performed in outpatient settings, RFA is gaining popularity in Asia to treat PTC and recurrence. Literature review to date has documented at least 150 patients who have undergone RFA for PTC, with reported 100% efficacy of tumor volume reduction ratio (VRR) $\geq 50\%$ (8-9). In a most recent report from Jeong et al, (9) RFA has produced excellent local tumor control for papillary macro- and microcarcinomas. In addition to the advantages listed above, complications of RFA are rare with only two cases related to vocal cord effects reported in literature so far, possibly attributed to nerve injuries during the ablation process; none life-threatening complications are reported.

Therefore we aim to assess the effectiveness of RFA on eliminating small papillary thyroid carcinomas, its ability for preservation of normal thyroid function and the overall safety of RFA procedure.

Rationale:

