RFA delivers a large yet focused amount of energy to an area of thyroid tissue that becomes “charred” and thus nonfunctional and nonviable. The residual tissue is slowly resorbed by the surrounding normal tissue, which leads to the resulting shrinkage of the original thyroid nodule (2, 10). Therefore this effect would be very desirable for a cancerous lesion, if it can be achieved safely. Our experience confirms that ultrasound-guided RFA is a clinically effective and safe outpatient treatment in patients with symptomatic or steadily growing benign, large, predominantly solid TNs. With appropriate expertise and world class infrastructure at Mayo Clinic this technique can be extended to treat papillary thyroid carcinomas and has the potential to become an alternative for the management of cancerous papillary thyroid nodules. Hence this pilot study is planned to test this hypothesis and secondarily to identify the safety of RFA for PTC, reveal factors predicting greater response, comparing the performance of RFA with other procedures, and timing of the additional RFA sessions, if needed.

[figure not shown]

Study Design and Procedure

STUDY DESIGN

This will be an open-label clinical trial that will target patients diagnosed with small papillary thyroid carcinoma (<1.5 cm) interested in RFA therapy. They will be assessed clinically and if they are considered candidates for non-surgical choices (observation or percutaneous ethanol injection) these patients will then be offered also the option of RFA therapy. We will treat them with RFA therapy of the PTC lesion and monitor the clinical response through changes in nodule size as measured by ultrasound (> 50% volume shrinkage at 18

Figure 1. RFA for PTC – Overview

months considered positive outcome) and/or development of cervical or distant metastatic disease. We expect that an individual will be thus in the study for a total of 18 months. The schematic depiction of the sequence of events during the trial is presented in figure 1.

The safety of the procedure will be also part of the primary objective, both local reactions as well as complications from RFA. We plan to enroll 5 patients. The study will take place at Mayo Clinic in Rochester, MN. We expect that we would be able to identify 15 cases/year that would qualify for this trial. Given the potential acceptance to enrollment we expect that it would take 18-24 months for the trial completion.

PROCEDURE:

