Subject Information

Target accrual is 5 patients. To achieve this number of subjects, we will access medical records for about 100 patients.

Subject population: Adults (≥ 18 years of age) who undergo evaluation at Mayo Clinic, Rochester for thyroid nodules.

Inclusion Criteria:

We will enroll patients that meet the following criteria:

- a. Nodule with Papillary thyroid carcinoma
 - i. Diagnosed by FNA cytology.
 - ii. Size < 1.5 cm
 - iii. Non-surgical therapy is considered acceptable by the treating physician
 - iv. Radiology evaluation deems the lesion amenable to RFA therapy with minimal risk of complication

Safety will be primordial and therefore the Interventional Radiology evaluation will influence decision to treat.

Exclusion Criteria:

All candidates meeting any of the following exclusion criteria at baseline will be excluded from study participation:

1. Clinical evidence for a multifocal papillary thyroid malignancy
2. Clinical evidence for local or distant metastatic disease
3. Pregnancy
4. Vocal cord paralysis on contralateral side
5. Coagulopathy or patients on anticoagulation therapy
6. Patients with prior neck surgery or neck radiation
7. Patients with neck anatomy that precludes easy access by RFA
8. Patients with comorbidities deemed too high of a risk for general anesthesia
9. Treatment with another investigational drug or intervention (within 6 weeks of planned RFA).
10. Current drug or alcohol use or dependence that, in the opinion of the site investigator, would interfere with adherence to study requirements.

11.

Research Activity

Check all that apply and complete the appropriate sections as instructed.

1. **X Drug & Device:** Drugs for which an investigational new drug application is not required. Device for which (i) an investigational device exemption application is not required; or the medical device is cleared/approved for marketing and being used in accordance with its cleared/approved labeling. (Specify in the study design and procedure section)
2. **X Blood:** Collection of blood samples by finger stick, heel stick, ear stick, or venipuncture.
3. **Biological specimens other than blood:** Prospective collection of human biological specimens by noninvasive means that may include: urine, sweat, saliva, buccal scraping, oral/anal/vaginal swab, sputum, hair and nail clippings, etc.

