Subject ID, subject code or any other person-specific unique identifying number, characteristic or code that can link the subject to their medical data		
Dates: All elements of dates [month, day, and year] directly related to an individual, their birth date, date of death, date of diagnosis, etc. Note: Recording a year only is not a unique identifier.	X	
Social Security number		
Medical device identifiers and serial numbers	X	
Biometric identifiers, including finger and voice prints, full face photographic images and any comparable images		
Web Universal Resource Locators (URLs), Internet Protocol (IP) address numbers, email address		

Street address, city, county, precinct, zip code, and their equivalent geocodes	X	
Phone or fax numbers	X	
Account, member, certificate or professional license numbers, health beneficiary numbers		
Vehicle identifiers and serial numbers, including license plate numbers		
Check 'None' when none of the identifiers listed above will be recorded, maintained, or shared during the conduct of this study. (exempt category 4)	 None	 X None

Data Analysis

Power analyses and study endpoints are not required for minimal risk research, pilot or feasibility studies.

No statistical information. *If checked, please explain:*

Data Analysis Plan:

Sample size has not been calculated as analysis will only include descriptive statistics. Results for continuous variables will be expressed as median and interquartile range, and for categorical variables as proportions.

References:

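### Are median, interquartile range and proportions too thin a summary for five patients?

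*Combined protocol and SAP*

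**What the plan says.** The combined protocol and SAP describes a single-group, open-label pilot. Study Design says "We plan to enroll 5 patients", and Subject Information agrees: "Target accrual is 5 patients".

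The Data Analysis Plan, under Data Analysis, has two sentences. The first says that the sample size was not calculated because the analysis is descriptive. The second says "Results for continuous variables will be expressed as median and interquartile range, and for categorical variables as proportions". No section mentions a listing by patient, a minimum and maximum, a quartile rule, a confidence interval or a confidence level.

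These summaries serve the following aims:

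- The hypothesis is that "RFA can control or eliminate small papillary thyroid carcinoma".
- Response is judged through "changes in nodule size as measured by ultrasound (> 50% volume shrinkage at 18" months, together with cervical or distant metastasis (Study Design).
- The aims section adds "We will also assess the stability of these changes (need for repeat therapy) and the safety of the RFA procedure".
- On safety, Study Design says "The safety of the procedure will be also part of the primary objective, both local reactions as well as complications from RFA".

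**The concern.** Five values are few, and a median with quartiles need not show the two extremes. For a hypothesis about controlling or eliminating a cancer, the extremes matter most: one tumour that grew, or one that disappeared. A responder count at the 50% threshold does not separate growth from shrinkage that falls short, and separate proportions do not show which tumour needed repeat treatment.

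Safety is part of the primary objective, so 0 of 5 complications could be printed as 0% with nothing to show how little five patients can exclude. In the same way, 5 of 5 responses would be printed as 100%, the figure that the background section cites from the literature: "at least 150 patients who have undergone RFA for PTC, with reported 100% efficacy of tumor volume reduction ratio" of at least 50%. At stake would be a reader who takes a very imprecise result for a firm one, or who never learns of one bad outcome.

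**Working it through.** The plan gives no interval, power or confidence level, so it has no figure of its own to reproduce. The inputs are n = 5 (Study Design; Subject Information) and the planned summaries (Data Analysis Plan). All patient values below are assumptions.

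**1. What the interquartile range shows at n = 5.** Under the linear rule the quartiles sit at positions 1 + 4 × 0.25 = 2 and 1 + 4 × 0.75 = 4. The range then runs from the 2nd to the 4th ordered value and leaves out the smallest and the largest.

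Assume volume reductions of 100, 95, 90 and 85%, with a fifth tumour at −40% (growth) or +40% (insufficient shrinkage). Both sets have median 90% and 4 of 5 responders. The lower quartile under nine common definitions is:

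| Quartile rule | Fifth value −40 | Fifth value +40 |
|---|---|---|
| Linear, inverted CDF, averaged inverted CDF | 85 | 85 |
| Closest observation | −40 | 40 |
| Interpolated inverted CDF | −8.75 | 51.25 |
| Weibull | 22.5 | 62.5 |
| Median-unbiased | 43.3 | 70.0 |
| Normal-unbiased | 45.9 | 70.9 |
| Hazen | 53.75 | 73.75 |

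As an example, the Weibull position is 6 × 0.25 = 1.5, which gives (−40 + 85)/2 = 22.5 and (40 + 85)/2 = 62.5.

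Growth is therefore masked under three rules of nine, and only when the non-responder is the worst of the five. A second invented pair tests elimination: 100, 95, 90, 85, 40 against 95, 95, 90, 85, 40. Its median, quartiles and responder count are identical under five rules of nine. So masking is possible, but it does not follow from the choice of median and interquartile range as such.

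**2. What a bare proportion withholds.** The two-sided exact (Clopper-Pearson) 95% limits at n = 5 are:

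- 0 of 5: the upper limit is 1 − 0.025^(1/5) = 1 − 0.478 = 52.2%.
- 5 of 5: the lower limit is 0.025^(1/5) = 47.8%.

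These limits depend only on the count and on n, so a proportion with n = 5 already determines them. Level and method are the analyst's choice. For 0 of 5, the one-sided exact 95% upper bound is 1 − 0.05^(1/5) = 45.1%, and the two-sided Wilson 95% upper limit is 43.4%.

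**3. What would change.** The additions would alter no median, quartile or proportion. The plan contains no test and no trial-level success threshold that an interval could inform. Metastasis and the need for repeat therapy are separate aims and can each be reported as a proportion, so tumour control is not judged from the volume quartiles alone.

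**The case for a change.** The best case for acting is that the additions cost a few lines and need no new data. A listing settled in advance commits the investigators to show every patient, whatever the result. A reader can rebuild an interval from x of 5, but cannot always rebuild five tumours from a median and two quartiles. Because no quartile rule is named, the same five assumed values (with −40%) could be published with a lower quartile anywhere from −40 to 85. Listings, ranges and intervals are also descriptive, so the pilot label does not argue against them.

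The arithmetic stands, and so does the practical advice: in a report on five patients, showing each one is sensible, and each proportion should carry its denominator. With four evaluable patients, for instance, 0 of 4 has a two-sided exact 95% upper limit of 1 − 0.025^(1/4) = 60.2%. What does not follow is that the plan is deficient without a sentence saying so. It leaves these displays open, and analysts of five patients would be expected to supply them.

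The comparison with the literature adds little. Taken at face value, 150 of 150 has a lower limit of 0.025^(1/150) = 97.6%. But the background figure is gathered from a literature review, uses a threshold of at least 50% and gives no assessment time, whereas this trial uses more than 50% at 18 months. The two percentages are not like for like. Nor is an exact interval neutral here: it treats as a random sample five patients who were interested in the procedure and were judged amenable to it at minimal risk of complication.

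**Conclusion.** The concern does not hold. Followed as written, the plan gives valid medians, quartiles and proportions for a pilot that openly limits itself to description. No estimate is biased, no stated conclusion rests on an omitted interval, and no decision would change.

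The intervals are wide (0 to 52.2% for 0 of 5; 47.8 to 100% for 5 of 5), but that width comes from having five patients, which the plan states twice, and not from the choice of summary. The loss of information about the extremes is real only under some quartile rules (three of nine for the growth example, five of nine for the elimination example) and with invented values. What remains is a reporting preference. This rests on the study staying descriptive and on results being reported with their number of patients.
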